Taking into account inclusion criteria (either newly diagnosed DM type 2 (drug naive) or inadequate glycemic control on previously prescribed monotherapy with metformin or inadequate glycemic control on previously prescribed monotherapy with any other oral antidiabetic drug) as well as non-intervention nature of the study it is proposed to use regression model to determine factors related to effect of Vipidia® on glycosylated hemoglobin (HbA1c) level dynamics. Sample size was calculated using SAS 9.3 proc power procedure (power for Multiple Linear Regression) for following parameters (fixed scenario elements):

Fixed Elements	Scenario
Method	Exact
Model	Random X
Number of Predictors in Full Model	7
Number of Test Predictors	1
Partial Correlation	0.1
Nominal Power	0.9
Alpha	0.05

Where the computational method set to exact, assumed distribution of the tested predictors set to joint multivariate normal distribution for the response and tested predictors, number of predictors in the full model, not counting the intercept assumed to be 7 (prior therapy of DM, sex, age, cardiovascular risk group, therapy type (monotherapy or combined therapy), baseline BMI, initial glycemic control), number of predictors in the reduced model, not counting the intercept assumed to be at least 1, level of significance of the statistical test set to 0.05, desired power of the test set to 0.9, partial correlation between the tested predictors and the response, adjusting for any other predictors in the model assumed to be at least 0.1 (small effect size).

For the denoted scenario, it is required to receive data from at least 1052 patients after the treatment of Vipidia® on glycosylated hemoglobin (HbA1c) level dynamics.

Computed N Total	
Actual Power	N Total
0.800	1052

Taking into account a possible dropout of 25%, to reach study objectives in regard to this endpoint, it is recommended to enrol at least 1403 patients into the study. Due to minimal difference between these two endpoints and number of subjects required, it is recommended to take bigger computed number of subjects (1403).

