Values with Z-score > 3.5 will be considered outliers for study variables considered normally distributed. Preliminary normality test (Shapiro–Wilk criterion) will be performed for these variables. In case if normality distribution hypothesis will be rejected based on Shapiro–Wilk test results, median and IQR (interquartile range) will be used for outlier identification. Values > 1.5 IQR far from median value will be considered outliers. No data will be excluded / modified based on outlier identification, however, additional medical context assessment for these data will be performed and data quality control / source verification check will be considered.

Interim Analyses

An interim analysis is planned to be performed as soon as first 350 patients have completed the study by achieving final study visit or discontinuing the study.

The reasons of performing this interim analysis is an importance of study data for medical society and commitment of the company to disclosure clinically relevant information to medical specialists.

At this level of the analysis study objectives listed in the sections 2.2.1-2.2.4 will be evaluated. The results will be provided according to reporting rules applicable for final statistical analysis and described in the Statistical Analysis Plan.

The interim analysis will be performed according to statistical procedures described in the sections # 05-10 of this Statistical Analysis Plan. No subgroup analyses are to be performed within interim analysis of the study.

The results of the interim analysis should be disclosed to public either through publication in medical scientific journal or within presentation at medical congress/conference.

After study is completed the complete study results are to be considered as prevailing the results of

interim analysis.

Multiple Comparisons/Multiplicity

When needed, corrections for multiplicity will be justified and performed according to Bonferroni. Overall alpha-level will be controlled and will not exceed 0.05. The interim analysis will not be taken into account within multiplicity adjustment procedure.

Examination of Subgroups

Some secondary endpoints will be analyzed in subgroups of patients with different clinical characteristics: demographic information, nicotine use, history of DM2T (see “EFFICACY ANALYSES” chapter).

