9.1. Statistical Analysis of the Primary Efficacy Variable(s)

Primary study outcome - change from baseline in glycosylated hemoglobin (HbA1c) level on Vipidia® therapy (V3). Taking into account inclusion criteria (either newly diagnosed DM type 2 (drug naive) or inadequate glycemic control on previously prescribed any oral antidiabetic drug) as well as non-intervention nature of the study it is proposed to use multifactorial regression model to determine factors related to effect of Vipidia® on glycosylated hemoglobin (HbA1c) level dynamics.

Change from baseline in glycosylated hemoglobin (HbA1c) level on Vipidia® therapy (V3) in subgroups with different clinical characteristics will be summarized using relevant descriptive statistics and analyzed using Multiple Linear Regression with following predictors: prior therapy of DM, sex, age, cardiovascular risk group, therapy type (monotherapy or combined therapy), baseline BMI, initial glycemic control, T2DM duration. No subgroup analyses will be performed within interim analysis of study data.

In addition, change from baseline in glycosylated hemoglobin (HbA1c) level will be assessed and evaluated using Mixed model repeated measures (MMRM) methodology [14, 15]. The multiple visits for each patient will be incorporated as repeated measures within each patient. Visit will be treated as a categorical predictor and baseline glycosylated hemoglobin (HbA1c) level and duration of T2 DM will be included as a covariate. An appropriate covariance structure will be selected to provide estimates (Least Square Means) of change from Baseline and to perform statistical analysis at Visit 3. The dose-response trend hypothesis test will be conducted using the appropriate contrast statement for a linear (ordinal dose) trend. In addition, Least Squares Means, the associated standard errors and 95% confidence intervals will be displayed by each individual dose group.

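### Where a multiplicity correction is applied, Holm's step-down procedure could replace Bonferroni: same family-wise control, never fewer rejections (optional improvement)

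*SAP*

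**What the plan says.** SAP section 5, under Multiple Comparisons/Multiplicity, states that, where needed, "corrections for multiplicity will be justified and performed according to Bonferroni". It adds: "Overall alpha-level will be controlled and will not exceed 0.05". The interim analysis is left out of the adjustment. No other correction method is named, and no family of tests is listed.

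The largest set of simultaneous tests on a stated objective is in section 9.1. There the change in HbA1c at V3 is "analyzed using Multiple Linear Regression with following predictors: prior therapy of DM, sex, age, cardiovascular risk group", followed by therapy type, baseline BMI, initial glycaemic control and diabetes duration. That makes 8 predictors. Section 9.1 mentions no adjustment for them.

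Section 2.4 sizes this objective with "number of predictors in the full model, not counting the intercept assumed to be 7", one predictor tested, a partial correlation of 0.1, "level of significance of the statistical test set to 0.05" and "desired power of the test set to 0.9". The result is 1052 evaluable patients, or 1403 enrolled after 25% dropout. Section 3 describes the study's methods as descriptive.

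**The concern.** Once a plan commits to a Bonferroni correction for a set of tests, a procedure with the same guarantee and at least as many rejections is available. Bonferroni compares every p-value with alpha divided by the number of tests. Holm relaxes the threshold after each rejection. Where several hypotheses in a corrected family are false, Bonferroni therefore gives up some power and gains no error control.

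The place where this could matter most is secondary objective 1, which asks how the HbA1c change depends on clinical characteristics. It is tested with several predictors at once, and its calculation set the enrolment figure. The paired tests at the end of section 9.2 are another possible place. In both, the loss arises only if a correction is actually applied.

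**Working it through.** **Inputs.** From SAP section 2.4: 1052 evaluable patients, partial correlation 0.1, alpha 0.05, 7 predictors with 1 tested. From section 9.1: 8 predictors. Assumed, because the SAP does not fix them: the 8 predictor tests form one corrected family, each is a single-coefficient test, the tests are independent, and each real factor has partial correlation 0.1.

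**Step 1: the plan's own figure.** By the Fisher-z approximation with 7 predictors, power = Φ(atanh(0.1) × √(1052 − 3 − 6) − 1.960) = Φ(0.1003 × 32.30 − 1.960) = Φ(1.280) = 0.90. The exact random-X calculation also gives 0.900, and 1052 / 0.75 = 1402.7, which rounds up to 1403. The sample size therefore reproduces as 90% power for one test at an unadjusted 0.05. (The output table in section 2.4 prints an actual power of 0.800, which does not fit; 80% would need about 788. That is a separate matter.)

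**Step 2: one test under Bonferroni.** The threshold is 0.05 / 8 = 0.00625. With 8 predictors, power = Φ(0.1003 × √1042 − 2.734) = Φ(0.505) = 0.69. The exact random-X value is 0.693.

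**Step 3: why Holm never rejects fewer.** Holm orders the p-values and compares the smallest with 0.05 / 8 = 0.00625, the next with 0.05 / 7 = 0.00714, then 0.05 / 6 = 0.00833, and so on up to 0.05, stopping at the first failure. Every threshold is at least 0.00625, so any p-value that Bonferroni rejects, Holm rejects too. Its family-wise control at 0.05 does not require independence.

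**Step 4: size of the gain.** Simulation with 8 independent tests at 1052 patients; average power per real factor:

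| Real factors | Bonferroni | Holm |
|---|---|---|
| 1 | about 0.70 | 0.70 |
| 2 | about 0.70 | 0.71 |
| 3 | about 0.70 | 0.72 |
| 4 | about 0.70 | 0.73 |
| 6 | about 0.70 | 0.77 |
| 8 | about 0.70 | 0.83 |

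To three decimals, the case of one real factor is 0.695 against 0.696. A factor benefits from Holm only when another has already been rejected, so the gain is negligible with one real factor and grows with the number.

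**Step 5: checks.** In 150,000 replicates per scenario Holm never rejected fewer hypotheses than Bonferroni. Simulated family-wise error was 0.049 for both methods with no real factor, and 0.025 (Bonferroni) against 0.041 (Holm) with 4 real, all below 0.05. With a correlation of 0.3 between the test statistics, average power was 0.70 against 0.73 (4 real) and 0.70 against 0.76 (6 real), so the pattern does not depend on independence.

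**The case against.** Four arguments can be made for leaving the sentence alone.

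- *Bonferroni is not wrong.* It delivers the promised limit, and nothing in the SAP contradicts it. This stands: the point concerns efficiency, not an error.
- *The correction is conditional.* It applies only where needed, and the SAP nowhere applies it to the section 9.1 coefficients. A reader might infer that the plan as written gives away power on the clinical-factor objective. The documents do not support that: section 2.4 sizes one test at an unadjusted 0.05 and section 9.1 is silent on adjustment. If those tests are not corrected, Bonferroni costs them nothing. This stands too, and it makes every figure above conditional.
- *The large gains need many real factors.* The 0.83 requires all eight predictors to be real, which the SAP does not assume. In the sizing scenario of one tested predictor, the gain is about 0.1 percentage point. Prior therapy has three categories in the inclusion criteria quoted in section 2.4 and may need more than one coefficient. These limits stand.
- *Bonferroni gives simple simultaneous confidence intervals, and the primary sizing is by interval half-width.* This is a fair reason to prefer it where adjusted intervals are wanted. But sections 3, 9.1 and 9.2 promise 95% intervals with no mention of adjustment, so no planned output would be lost.

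The objection does not remove the core: for hypothesis tests, wherever a correction is used, Holm is at least as powerful at the same error limit.

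**Conclusion.** The point holds as an optional, low-cost improvement. Section 5 names Bonferroni as the only correction method, and Holm would meet the same 0.05 limit with never fewer rejections.

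If the 8 predictor tests were corrected, the gain in average power per real factor would be almost nothing with one real factor, about 1 percentage point with two, roughly 2 to 4 points with three or four, and larger only with six or more. These figures rest on the four assumptions listed above, none of which the SAP fixes.

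Two stronger readings are not supported. One is that Holm would repair the fall from 0.90 to about 0.70. That fall comes from sizing at an unadjusted 0.05 and then correcting for 8 tests, and with few real factors Holm barely changes it. The other is that adopting Holm means the predictor tests should become a corrected family. That is a separate trade-off: it would lower power per factor from 0.90 unadjusted to about 0.70 to 0.73 with 1 to 4 real factors, and it should not be presented as costless.

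**What to change.** In section 5, under Multiple Comparisons/Multiplicity, replace the reference to Bonferroni with *according to the Holm step-down procedure*, wherever a correction is applied. Leave the planned unadjusted 95% confidence intervals unchanged.

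Do not use this edit to decide whether the section 9.1 regression tests are a corrected family; that needs its own decision, with the power consequences shown above in view.

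The cost is one phrase, with no additional patients or data. The one drawback is that Holm has no simple matching simultaneous confidence intervals, which matters only if adjusted intervals are later wanted.

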6. STUDY POPULATION CHARACTERISTICS

Patient Disposition

Data regarding how many patients reached the various stages of the trial, how many dropped out, discontinued the treatment and for what reasons (death, AEs, treatment failure, withdrew consent, lost to follow-up) will be presented for each subgroup and for study in bulk. Standard CONSORT diagram describing study patient flow will be provided.

As an open label study, there is limited opportunity for patients to receive incorrect drug and/or to inadvertently break the blind. However, in order to assess the conduct of the study, major protocol violations will be summarized and listed. Such violations will be defined prior to the first reporting event but will include at least the following:

- Non compliance with inclusion criteria
- Non compliance with exclusion criteria
- Non compliance with study treatment
- Use of disallowed concomitant medication

7. DEMOGRAPHICS AND OTHER BASELINE CHARACTERISTICS

Demographics

Unless specified otherwise, all demographic and other baseline characteristics will be summarized for the All Patients Enrolled population of subjects.

All demographic and other Baseline characteristics will be summarized for overall analysis population. It's planned to describe all baseline patients characteristics within an interim analysis as well.

Medical History, Concomitant Diseases

Baseline medical conditions (comorbidities) reported in the Medical History Case Report Form (CRF) will be coded using the Medical Dictionary for Regulatory Activities (MedDRA) and summarized by

Dosage cohort group for all treated patients on two levels: event level and subject level. For event level all comorbidities reported on the CRF will be summarized in the first table (by Dosage cohort group), and the second table will summarize only comorbidities that were ongoing on the date of baseline visit.

For subject level reporting, study subjects with at least one comorbidity (by Preferred Term within System Organ Class Term) will be summarized by Dosage cohort group, as well as study subjects with at least one comorbidity that were ongoing on the date of baseline visit will be summarized by Dosage cohort group.

Prior and Concomitant Medications

Prior medications, taken after informed consent is signed, and before the first dose of study drug, will be summarized by Dosage cohort group.

Concomitant medications are medications other than study drug that a patient reports taking between the first dose and last dose of study drug. These include medications that are taken before the first dose of study drug and continue to be taken during study treatment. Concomitant medications will be summarized by Dosage cohort group.

All prior and concomitant medications will be coded using Anatomical Therapeutic Chemical (ATC) dictionary and reported by the 2nd level by Dosage cohort group.

8. MEASUREMENT OF EXPOSURE TO STUDY DRUG

The total duration of exposure is defined as the time interval between the first dose and the last dose, inclusive, of study drug based on the patient study drug dosing information. In case if significant (e.g. >5%) number of subjects will switch doses during the study, additional tabulation by dose will be performed (these subgroups will be defined as dosage cohorts and will be used for data tabulation / presentation purposes). Total duration (weeks) of exposure to study drug in the All Patients Enrolled population will be summarized by descriptive statistics (ie, total number, mean, standard deviation, median, minimum, and maximum) - see "Summary of study data".

Data for study subjects' compliance will be summarized and tabulated by visit.

Area under curve as product of compliance for distinct period (e.g. time between visits) and duration of this period) will be calculated and summarized.

This evaluation will be performed both for overall and for interim analysis of the study.

9. EFFICACY ANALYSES

Unless stated otherwise all Patients Enrolled population will be used for the primary, supportive primary, secondary, and exploratory efficacy analyses conducted for the study.

Unless stated otherwise, all efficacy variables will be summarized in convenience with "Summary of study data". All efficacy data, including selected derived data will be included in data listings.

For performing interim analysis data of first 350 enrolled patients will be used for the efficacy analyses listed in this section. For the interim efficacy analyses the methodology listed in this section is planned to be used.

9.1. Statistical Analysis of the Primary Efficacy Variable(s)

Primary study outcome - change from baseline in glycosylated hemoglobin (HbA1c) level on Vipidia® therapy (V3). Taking into account inclusion criteria (either newly diagnosed DM type 2 (drug naive) or inadequate glycemic control on previously prescribed any oral antidiabetic drug) as well as non-intervention nature of the study it is proposed to use multifactorial regression model to determine factors related to effect of Vipidia® on glycosylated hemoglobin (HbA1c) level dynamics.

Change from baseline in glycosylated hemoglobin (HbA1c) level on Vipidia® therapy (V3) in subgroups with different clinical characteristics will be summarized using relevant descriptive statistics and analyzed using Multiple Linear Regression with following predictors: prior therapy of DM, sex, age, cardiovascular risk group, therapy type (monotherapy or combined therapy), baseline BMI, initial glycemic control, T2DM duration. No subgroup analyses will be performed within interim analysis of study data.

In addition, change from baseline in glycosylated hemoglobin (HbA1c) level will be assessed and evaluated using Mixed model repeated measures (MMRM) methodology [14, 15]. The multiple visits for each patient will be incorporated as repeated measures within each patient. Visit will be treated as a categorical predictor and baseline glycosylated hemoglobin (HbA1c) level and duration of T2 DM will be included as a covariate. An appropriate covariance structure will be selected to provide estimates (Least Square Means) of change from Baseline and to perform statistical analysis at Visit 3. The dose-response trend hypothesis test will be conducted using the appropriate contrast statement for a linear (ordinal dose) trend. In addition, Least Squares Means, the associated standard errors and 95% confidence intervals will be displayed by each individual dose group.

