2. PROTOCOL SUMMARY

2.1 Study design and conduct

This is a local, prospective, multicentre, non-interventional, observational study in adult patients with T2DM diagnosis.

Due to the observational design, patient visits to the referring physician are not pre-specified by the study protocol, but will follow usual clinical practice. All patient-care decisions, including diagnostic and therapeutic interventions, will be made by and conducted at the discretion of the participating study physicians according to their clinical judgment and the local standard of medical care.

[figure not shown]
Start of the study is defined as the date of the start of data collection (first patient signed ICF for data collection).

End of the enrolment (Last Patient First Visit) is defined as the date when the last patient signs ICF and enrolled in the study.

End of the patient observation (Last Patient Last Visit) is defined as the last date when the patients are observed in the scope of the study.

End of study (end of data collection) is defined as the date when the last data point is collected. Up to this date all the CRFs should be completed and all the data clarifications (queries) should be done.

The study is considered to be completed after the database is closed, the final statistical analysis is performed and the study report is written. The study report must be signed within 12 months after the collection of the last data point.

It's planned that interim statistical analysis of study data will be performed as soon as 350 first study patients have completed the study by achieving final study visit or discontinuing their participation.

Term	Baseline visit (V1)	Observational visit (V2)	Final visit (V3)
Inclusion/exclusion criteria	X		
Signed Informed consent form	X		
Date of visit	X	X	X
Demographic information	X		
Medical history including history of DM2T	X		
Concurrent medical conditions	X		
Physical examination and vital signs*	X	X	X
Study medication	X	X	X
Laboratory tests and instrumental exams*	X	X	X
Concomitant treatment (including DM2T treatment)	X	X	X
Healthcare resources utilization		X	X
Adverse events		X	X

For study details and study assessment's schedule see the Protocol of the Study.

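### The coefficient for initial glycemic control in the HbA1c-change regression cannot be read as a factor in the effect of Vipidia, because it cannot be told apart from mathematical coupling and regression to the mean

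*SAP*

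**What the plan says.** Section 9.1 takes the change in HbA1c from baseline to V3 as the outcome and proposes a multifactorial regression "to determine factors related to effect of Vipidia". The list of eight predictors ends with "baseline BMI, initial glycemic control, T2DM duration". Section 2.4 gives the same purpose ("it is proposed to use regression model to determine factors related to effect of Vipidia"). It counts initial glycemic control among its seven predictors (disease duration is the one added in 9.1) and sizes the study for a test of one predictor at alpha 0.05 and power 0.9. Secondary objective 1 and secondary endpoint 1 rest on this analysis.

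Initial glycemic control is not defined in either section. The repeated-measures model later in 9.1 names its term explicitly: "baseline glycosylated hemoglobin (HbA1c) level and duration of T2 DM will be included as a covariate".

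The design is described in section 2.1: "This is a local, prospective, multicentre, non-interventional, observational study in adult patients with T2DM diagnosis". All patients are prescribed Vipidia and no comparator is described. Patients enter as newly diagnosed or with "inadequate glycemic control on previously prescribed any oral antidiabetic drug". The SAP says nothing about coupling between a change score and its baseline, or about regression to the mean.

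**The concern.** If initial glycemic control is baseline HbA1c, the outcome is V3 minus that value and the predictor is that same value. Part of the association is then built in. Patients who happen to measure high at baseline tend to measure lower later, whatever the drug does. A comparator group would show how much of the slope arises without the drug, but none is described.

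The SAP assigns this coefficient a meaning, since the model is there to find factors related to the drug's effect and this variable is one of the candidates. Read that way, secondary objective 1 would very probably report that patients with worse initial control respond better to Vipidia, and this analysis could not support that statement.

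**Working it through.** **Inputs from SAP section 2.4.** Correlation between visits rho = 0.35; SD up to 0.70; half-width 0.05; 1037 pairs; regression N = 1052 with seven predictors, one tested, partial correlation 0.1, alpha 0.05, power 0.9.

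**The plan's own figures.**
- With one SD of 0.70 at both visits, the SD of change is 0.70 × sqrt(2 × (1 - 0.35)) = 0.798. The exact conditional calculation for half-width 0.05 then gives 1037 pairs at probability 0.900, as stated. If 0.70 were the SD of the change itself, the answer would be 805. The plan's calculation therefore assumes equal SDs at the two visits.
- Exact random-predictor power for a partial correlation of 0.1 with six other predictors is 0.900 at N = 1052, as intended. The power of 0.800 printed beside that N is a separate slip. With eight predictors N becomes 1053.

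**Null case: the same drug effect in every patient.** Let k = SD(V3)/SD(V1).
- Slope of change on baseline = rho × k - 1
- Correlation = (rho × k - 1) / sqrt(1 + k² - 2 × rho × k), which for k = 1 is -sqrt((1 - rho)/2)
- t = r × sqrt((n - 2)/(1 - r²))

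With rho = 0.35, k = 1 and n = 1052:
- slope = 0.35 - 1 = -0.65
- r = -sqrt(0.325) = -0.570, so R² = 0.325
- t = -0.570 × sqrt(1050/0.675) = -22.5

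A simulation of 500 studies with N = 1052, SD 0.70, rho 0.35, a constant effect of -0.8 (assumed; its size does not alter the slope) and seven unrelated predictors gave mean slope -0.65, mean t -22.6 and mean partial correlation -0.57. The largest p-value was about 3e-64.

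**Sensitivity.** Correlations and SD ratios other than rho = 0.35 and k = 1 are assumed.

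| rho | k | slope | r |
|---|---|---|---|
| 0.2 | 1.0 | -0.80 | -0.63 |
| 0.35 | 0.8 | -0.72 | -0.69 |
| 0.35 | 1.0 | -0.65 | -0.57 |
| 0.35 | 1.2 | -0.58 | -0.46 |
| 0.5 | 1.0 | -0.50 | -0.50 |
| 0.8 | 1.0 | -0.20 | -0.32 |
| 0.9 | 1.0 | -0.10 | -0.22 |
| 0.8 | 1.2 | -0.04 | -0.06 |

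With equal SDs, t at N = 1052 is still about -18.7 at rho 0.5, -10.8 at 0.8 and -7.4 at 0.9. It becomes small (about -1.8) at rho 0.8 with k = 1.2, that is, with a high correlation and an SD that rises at V3.

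**Other definitions of the variable.**
- Baseline HbA1c split at its median: the poorly controlled half falls 0.72 points more, r about -0.45, t about -16.6, under an identical effect.
- Another glycaemic measure with correlation q to baseline HbA1c: if it relates to V3 HbA1c only through baseline HbA1c, r = -0.57 × q. This gives -0.17 at q = 0.3 and -0.40 at q = 0.7 (both values assumed). It would be weaker for a measure that tracks mainly the stable part of a patient's HbA1c.

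**What is not affected.** In the same simulation the other coefficients were identical whether the outcome was change or V3 HbA1c (largest difference about 6e-14), and an unrelated predictor kept a 5% error rate. Taking V3 as the outcome merely moves the baseline slope from -0.65 to +0.35, with a null value of 1 in place of 0, so it does not solve the problem.

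**The case against.** **Adjusting for baseline is correct practice.** This stands. The term belongs in the model and the other seven coefficients are sound in this respect. The fault lies in the meaning given to this one coefficient.

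**The SAP never says that initial glycemic control is baseline HbA1c.** This stands too. Section 9.1 names baseline HbA1c explicitly in its repeated-measures model, so the different wording may mean a category or another measure. The slope of -0.65 and t of -22 are therefore conditional on the natural reading. The artefact is weaker for other definitions, but the lack of a definition does not remove it.

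**The study is descriptive, and *related to* need not mean *caused by*.** This stands in part. That patients with a higher baseline fall more is a true description, and the SAP nowhere says the result will guide treatment. But section 2.4 sets alpha and 90% power for testing a predictor, and both sections refer to the effect of the drug, which goes beyond description.

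**A real baseline-dependent effect may exist.** It may. A reader might infer from the arithmetic that any such finding would be nothing but regression to the mean. The documents do not support that. A real effect could coexist with the artefact, and this model cannot separate them.

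**Conclusion.** Wrong as written, in one limited respect. The coefficient for initial glycemic control cannot be distinguished from mathematical coupling and regression to the mean, so it cannot serve the purpose that sections 2.4 and 9.1 give it. Under the SAP's planning inputs the spurious correlation is about -0.57, more than five times the 0.1 the study is sized to detect (0.57/0.1 = 5.7).

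The size rests on three assumptions: the variable is continuous baseline HbA1c, the between-visit correlation is 0.35, and the SDs at the two visits are equal. The last two are those of the SAP's sample size calculation.

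A reader might go further and conclude that the whole regression or the primary result is compromised. That does not follow: the coupling touches one of eight coefficients and leaves the mean change as it is.

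**What to change.** In section 9.1, and in matching words in section 2.4:

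1. Define initial glycemic control: which measure, and whether it is continuous or categorised.
2. State that it enters as an adjustment covariate only.
3. State that neither its coefficient nor differences in change between subgroups of initial control will be interpreted as a factor related to the effect of Vipidia.

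Oldham's test (change against the average of the two visits) should not be substituted. Its correlation under a constant effect is (k² - 1)/sqrt((1 + k²)² - 4 × rho² × k²), which is zero only for equal SDs. At rho = 0.35 it is -0.19/sqrt(1.81² - 4 × 0.1225 × 0.81) = -0.11 for k = 0.9, and in simulation a 10% SD difference made it reject more than 90% of null studies. Selection on inadequate control also breaks it. With the lowest 10% of baseline values removed (an assumed cut), it rejected about 100% of null studies at rho 0.35 and about 90% at 0.8, in the direction opposite to the coupling artefact.

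The cost is one or two sentences and the loss of one reported predictor. Data collection and sample size do not change.

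### Power of 0.9 per factor and an overall alpha of at most 0.05 cannot both hold across the eight-factor HbA1c regression that sets enrolment

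*SAP*

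**What the plan says.** Section 2.4 sizes the secondary objective (HbA1c change in relation to baseline characteristics) with a multiple linear regression. The "number of predictors in the full model, not counting the intercept assumed to be 7" are prior therapy, sex, age, cardiovascular risk group, therapy type, baseline BMI and initial glycemic control. The entry for "Number of Test Predictors" is 1. The partial correlation is set "adjusting for any other predictors in the model assumed to be at least 0.1 (small effect size"), the "level of significance of the statistical test set to 0.05" and the "desired power of the test set to 0.9". The result is 1052 evaluable patients, raised to 1403 for 25% dropout. The SAP takes 1403 over the 1383 from the primary precision calculation because it is the larger. The output table beneath the inputs prints an actual power of 0.800.

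Section 9.1 uses the regression to determine which factors relate to the effect on HbA1c. Its predictor list has the same seven and one more: "baseline BMI, initial glycemic control, T2DM duration". No factor is named as the one of main interest.

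Section 5, under Multiple Comparisons/Multiplicity, says that, where needed, "corrections for multiplicity will be justified and performed according to Bonferroni. Overall alpha-level will be controlled and will not exceed 0.05". It leaves the interim analysis out of the adjustment. It does not mention the regression or give a number of tests.

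On prior therapy, section 2.4 describes the inclusion routes as "either newly diagnosed DM type 2 (drug naive) or inadequate glycemic control on previously prescribed monotherapy with metformin", with monotherapy on another oral drug as a third route. Section 9.1 describes two: drug naive, or inadequate control on any oral antidiabetic drug. Neither section fixes the coding of this predictor.

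**The concern.** The calculation that sets enrolment covers one test at the full 0.05. The analysis it supports looks across eight factors, and another section of the same document limits the overall alpha to 0.05. If each of the eight is tested at 0.05, overall alpha is not held. If alpha is divided, the power for each factor is not 0.9. The SAP does not say which promise gives way, so the choice could be made after the data are seen. A reader of the report could then take the 0.9 in section 2.4 as the power behind every factor, including those found non-significant.

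**Working it through.** **Inputs.** From section 2.4: N = 1052, k = 7 predictors, t = 1 tested, partial correlation 0.1 (partial R² = 0.01), alpha 0.05, random-X model, dropout 25%. From section 9.1: k = 8. Assumed, because the SAP does not give them: the Bonferroni divisor, and a partial R² of 0.01 for any joint test with 2 degrees of freedom.

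**Formula.** Given the predictors, the partial F statistic is noncentral F with t and N − k − 1 degrees of freedom and noncentrality [R²/(1 − R²)] × W, where W is chi-square with N − 1 − (k − t) degrees of freedom. Power is the probability of exceeding the critical F value, averaged over W.

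**Step 1, the SAP's own figure.** With k = 7 and t = 1, W has 1052 − 1 − 6 = 1045 degrees of freedom, and the mean noncentrality is (0.01/0.99) × 1045 = 10.56. Power is 0.9001. The smallest N reaching 0.9 is 1052, so the sample size reproduces. Enrolment is 1052/0.75 = 1402.7, or 1403. A power of 0.80 would need only 788, so the printed 0.800 does not belong to N = 1052.

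**Step 2, the eighth predictor.** With k = 8, t = 1 and alpha 0.05, power is 0.8998. Reaching 0.9 takes 1053 patients, one more. Even 12 parameters give 0.8987. The difference between the two lists has no practical effect on power.

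**Step 3, eight tests at 0.05 each.** If the tests were independent and all null, the chance of at least one false positive would be 1 − 0.95⁸ = 0.34. Independence is an assumption, but it shows that testing each factor at 0.05 does not hold overall alpha at 0.05.

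**Step 4, dividing alpha (N = 1052, k = 8, t = 1).**

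| Alpha per test | Power per single-df factor |
|---|---|
| 0.05 | 0.90 |
| 0.05/2 = 0.025 | 0.84 |
| 0.05/3 = 0.0167 | 0.80 |
| 0.05/8 = 0.00625 | 0.69 |

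The shortfall does not depend on choosing eight: a divisor of two already takes power below 0.9. Restoring 0.9 at 0.05/8 would need 1612 evaluable patients (1612/0.75 = 2149.3, or 2150 enrolled).

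**Step 5, a three-level prior-therapy factor, if it is coded that way.** With two indicator terms k = 9, and a joint test has t = 2. At an assumed partial R² of 0.01 for the whole factor, power is 0.835 at alpha 0.05 and 0.583 at 0.05/8. A single-df test in the same nine-parameter model has power 0.8995, so it is the joint test that costs power and not the extra parameter.

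**The case against.** The case for leaving section 2.4 alone is substantial. The calculation is correct for what it states: one predictor, one test, alpha 0.05. It makes no promise about a simultaneous search. The Bonferroni correction is conditional, is not assigned to the regression and has no divisor, so 0.69 describes an analysis that the SAP does not specify. The study is described as descriptive, the factor analysis is a secondary objective, and the primary calculation alone asks for 1383 patients, only 20 fewer.

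Most of this stands. It rules out three stronger readings that a reader might infer:

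- That the change from seven to eight predictors undermines the power. It costs 0.03 percentage points.
- That the model certainly contains a three-level factor. Section 2.4 suggests three groups and section 9.1 two, and no coding is given.
- That Bonferroni over eight is the planned analysis, so that the 0.9 is shown to be lost. The SAP fixes neither the scope of the correction nor the number of tests.

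What the objection does not answer is the sentence on overall alpha. Only the correction is conditional. The statement that overall alpha will be controlled at 0.05 is not, and the only exemption named is the interim analysis. Either the regression is covered, and 0.9 per factor is too high, or it is not covered, and the SAP should say so.

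**Conclusion.** The point holds as a conflict between two stated properties, not as an arithmetic error in the sample size. N = 1052 is right for a power of 0.90 for one pre-named single-df predictor at unadjusted 0.05. Across an eight-factor search with overall alpha of at most 0.05, power per single-df factor would be about 0.69 (Bonferroni over eight, partial correlation 0.1). A divisor of two would give 0.84. These figures rest on an assumed number of tests. If prior therapy has three levels and is tested jointly at a partial R² of 0.01, also assumptions, power for that factor is about 0.83 without adjustment and 0.58 at 0.05/8. The mismatch in the predictor lists is real but matters only as a matter of consistency. The printed 0.800 is a separate error in the same table. None of this calls the enrolment target into question.

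**What to change.** List the same eight predictors in sections 2.4 and 9.1, and state how prior therapy and the other categorical factors are coded and with how many degrees of freedom. Then choose one of two positions:

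1. Keep the factor tests confirmatory. State the number of tests under the multiplicity rule, and restate the power as about 0.90 for one pre-named single-df predictor at unadjusted 0.05 and about 0.69 per predictor under Bonferroni over eight. Give a figure for any joint multi-df test only after its coding is fixed.
2. Declare the factor search exploratory and outside the overall-alpha statement in section 5, reported with unadjusted 95% confidence intervals.

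In either case, correct the printed actual power of 0.800 to 0.900. The cost is SAP wording only. Under the first position a stated power becomes less favourable. Enrolment of 1403 need not change.
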